## 5. Study Population

## a. Number of Subjects

There will be 22 subjects enrolled from the Neuro ICU. We will end enrollment at the end of the 2019 calendar year, whether or not the enrollment target has been met. We will compare the hospital course of the prospectively enrolled e-stim patients with pooled, de-identified historical patients identified from quality improvement databases maintained by the Neurosciences ICU group.

#### b. Inclusion and Exclusion Criteria

Patients admitted to the Neuro ICU will be screened for eligibility through a review of medical records in Epic by study co-investigators who are also clinicians in the Neuro ICU. Screening data will be destroyed at the end of the study.

## Inclusion criteria

- Age ≥18 and ≤100
- Admission to the Neuro ICU for care for a neurologic illness requiring critical care
- Prognosis for prolonged ICU stay and/or prolonged intubation as evidenced by at least one pre- morbid risk factor: age ≥ 65 years, major medical co-morbidity (ex: heart failure, chronic obstructive pulmonary disease, chronic renal insufficiency, diabetes, poorly controlled hypertension, etc.), or severe acute critical illness (APACHE II >12)

## c. Vulnerable Populations

We will not be enrolling any vulnerable populations, such as minors, pregnant women, or prisoners, other than decisionally impaired adults. Inclusion of decisionally impaired adults is discussed in greater detail in the Consent Process and Adults Unable to Consent sections of the protocol.

## d. Setting

Neurosciences ICU (Neuro ICU).

## e. Recruitment Methods

Patients admitted to the Neuro ICU will be screened for eligibility through a review of medical records in Epic by study staff, and approached for consent. Patients with prognosticated prolonged stay will be approached on day 2 to 5 of their ICU stay for enrollment. If patients have reversible exclusion criteria, such as hemodynamic instability or elevated intracranial pressures, they will be rescreened daily for potential enrollment until day 7.

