# 2. Objectives

The purpose of this pilot trial is to estimate the effect of electrical stimulation (e-stim) to the bilateral quadriceps on duration of intubation, intensive care unit (ICU) and hospital length of stay, and functional recovery in the Neuro ICU in comparison to historical matched controls. The objective of this initial pilot and feasibility study to estimate the effect size to power a future full scale randomized controlled trial of this intervention and to optimize study logistics for a future full scale trial. We propose the following specific aims:

**Specific Aim 1 - Feasibility:** Determine whether at least 80% of planned treatments can be performed as described, and that there is adequate patient population meeting inclusion criteria available for study

**Specific Aim 2 - Efficacy:** Evaluate efficacy of e-stim by comparing length of ICU stay (days from admission to "intermediate level of care" ordered in Epic) and duration of intubation (days) of subjects (for those who were intubated) to that of historical controls.

**Specific Aim 3 - Exploratory:** Evaluate functional recovery (measured by modified Rankin Scale [mRS] and Extended Glasgow Outcome Scale [GOSE] at Neuro ICU discharge) of subjects compared to that of historical controls.

**Hypothesis:** We hypothesize that e-stim treatment will be feasible in the Neuro ICU and will reduce the length of hospital stay and intubation and improve functional recovery.

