To date, no published trials have evaluated the impact of electrical stimulation on patients in the Neuro ICU and none have evaluated the impact specifically on length of ICU and hospital stay. We therefore propose a trial to estimate the effect of electrical stimulation (e-stim) to the bilateral quadriceps on duration of intubation, ICU and hospital length of stay, in 22 patients in the OHSU Neuro ICU and compare these outcomes with historical pooled de-identified data from the Neuro ICU quality/safety database with regards to age, sex, illness severity, comorbidities and other predictors of LOS.

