## 4. Study Design

The study will be a prospective, feasibility pilot study to estimate the effect size to power a future, full scale randomized controlled trial of electrical stimulation. The information learned in the pilot will help the team optimize study logistics for a future full-scale trial. The historical controls used for comparison will be from pooled, de-identified data pulled from quality improvement databases maintained by the Neurosciences ICU group. The research team will not have access to identifiable data for the historical controls—only means from the historical controls on data such as length of stay and hospital costs.

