#### **Historical Controls**

The Neuro ICU administration maintains databases for the purpose of safety and quality improvement. We propose to query this existing database to identify patients cared for in the Neuro ICU during the year 2016 that possess similar demographics and illness characteristics as our inclusion criteria. The ICU quality group will abstract data for us. The research team will not have access to identifiable data for the historical controls—only means from the historical controls on data such as length of stay and hospital costs. The information will be extracted using automated means from this database and Epic to capture average length of stay and length of ventilator support for the purposes of comparison as "historical controls". We will not be performing individual chart review.

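### E-stim patients must still be in the Neuro ICU on day 2–5 to enter, but the 2016 control query has no matching condition; taken alone, this lengthens e-stim ICU stay relative to controls

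*Combined protocol and SAP*

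**What the plan says.** **Entry to the e-stim group.** Section 5e (Recruitment Methods): "Patients with prognosticated prolonged stay will be approached on day 2 to 5 of their ICU stay for enrollment". For patients with reversible exclusions, "they will be rescreened daily for potential enrollment until day 7".

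**Outcome clock.** Section 2, Specific Aim 2, evaluates efficacy by "comparing length of ICU stay (days from admission to" the order for intermediate-level care. Days before enrolment therefore count.

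**Inclusion criteria.** Section 5b asks for "Prognosis for prolonged ICU stay and/or prolonged intubation as evidenced by at least one" risk factor: older age, a major comorbidity, or an APACHE II score above 12. This is predicted stay, not days already spent in the unit.

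**Controls.** Section 6 (Historical Controls) will look for "patients cared for in the Neuro ICU during the year 2016 that possess similar demographics and illness characteristics as our inclusion criteria". On the mechanics: "The information will be extracted using automated means from this database and Epic to capture average length of stay". Section 3 adds that the comparison is made "with regards to age, sex, illness severity, comorbidities and other predictors of LOS". Under Section 4 the team receives "only means from the historical controls on data such as length of stay and hospital costs".

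Section 2 calls the controls matched, and Section 8 lists covariates. Neither states a minimum stay for controls or uses time from admission to enrolment.

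**The concern.** A patient who left the Neuro ICU on day 1 cannot be in the e-stim group, and one who left on day 3 can be in it only if approached by then. The same two patients, had they been admitted in 2016 with a qualifying risk factor, satisfy the control description in Section 6. One group's stays are cut off from below (left-truncated) and the other's are not, while both are measured from admission. That gives a difference in mean stay with no treatment effect at all.

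Sections 2 and 4 give the pilot's purpose as estimating an effect size to power a randomised trial. An estimate pulled towards zero by the entry rule could inflate that trial or lead to a useful treatment being dropped. This error does not shrink with more patients. The regression in Section 8 would not remove it, because no listed covariate carries the entry condition. The team, receiving only control means, cannot apply the condition itself; it has to be in the query.

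**Working it through.** **Inputs from the documents.** Entry on ICU day 2–5, extended to day 7 (Section 5e); stay counted from admission (Section 2); 22 e-stim patients and 23 controls (Section 8, Power Calculation).

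**Inputs that must be assumed.** The documents give no distribution of ICU stay and no pattern of enrolment days. I take five stay distributions and several entry patterns. Being approached on day d means an elapsed time t of between d−1 and d days, so each result is a range from t = d−1 to t = d.

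**The plan's own figures.** The plan gives no figure for this bias. For scale, Section 8 plans 113 per group to detect 10 versus 7 ventilation days with 80% power at 0.05. Taking the test as two-sided, this implies a common SD of 3/(1.960 + 0.842) × √(113/2) ≈ 8.0. That SD concerns ventilation days; I borrow it only as a plausible spread for ICU stay. The pilot size reproduces: 20% × 226 = 45.2, against 22 + 23 = 45.

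**Formula.** With no treatment effect,

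artefact = Σ E[LOS; LOS > t] / Σ P(LOS > t) − E[LOS],

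summed over equally likely approach days, where E[LOS; LOS > t] is the part of the mean contributed by stays longer than t. It is positive whenever some comparable patients leave before t.

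**Worked case: lognormal, mean 10, SD 8, approach uniform on days 2–5.**

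| t | P(LOS > t) | E[LOS; LOS > t] |
|---|---|---|
| 1 | 0.9983 | 9.9986 |
| 2 | 0.9736 | 9.9585 |
| 3 | 0.9131 | 9.8047 |
| 4 | 0.8292 | 9.5098 |
| 5 | 0.7369 | 9.0942 |

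- t = d−1 (rows 1–4): 39.2716/3.7142 − 10 = 0.57 days; share of controls failing the rule 1 − 3.7142/4 = 7.1%.
- t = d (rows 2–5): 38.3672/3.4528 − 10 = 1.11 days; share failing 1 − 3.4528/4 = 13.7%.

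**All assumed cases (days).**

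| Stay distribution (mean, SD) | All on day 2 | Uniform 2–5 | All on day 5 | Controls failing, uniform |
|---|---|---|---|---|
| Lognormal (14, 8) | 0.00 | 0.06–0.18 | 0.20–0.49 | 0.6–1.8% |
| Lognormal (12, 8) | 0.00–0.04 | 0.22–0.50 | 0.62–1.19 | 2.3–5.5% |
| Lognormal (10, 8) | 0.02–0.23 | 0.57–1.11 | 1.47–2.34 | 7.1–13.7% |
| Lognormal (6, 6) | 0.23–1.04 | 1.42–2.42 | 3.28–4.49 | 26–39% |
| Exponential (10) | 1.0–2.0 | 2.38–3.38 | 4.0–5.0 | 22–29% |

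With 10% approached on each of days 6 and 7 and the rest uniform on days 2–5, the lognormal (10, 8) case becomes 0.92–1.51 days.

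**Against sampling error.** With SD 8, SE = 8 × √(1/22 + 1/23) = 2.39 days. The uniform lognormal (10, 8) artefact is 0.57/2.39 = 0.24 to 1.11/2.39 = 0.46 SE.

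**Effect on the estimate.** In a simulation of 22 versus 23 patients (lognormal (10, 8), t = d, 20,000 runs) with a true 30% cut in stay after enrolment, the mean difference was −1.18 days with no control rule and −2.31 days with the same rule in both groups.

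**The case against.** **Section 6 is silent; it does not plan to include early leavers.** The quality group writes the operating rules, and the plan speaks of matching and of predictors of stay. This stands in part: the bias depends on how the query is run. But the day 2–5 window is in the recruitment section, not the inclusion criteria, so a query faithful to Section 6 would not contain it.

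**The net direction is not known.** A reader might infer that the Aim 2 comparison as a whole is biased against e-stim and so could not show a false benefit. The documents do not support that. Section 5b excludes unstable patients, those with raised intracranial pressure and those with severe oedema from the e-stim group, and does not say the same for controls. If such patients stay longer, the control mean rises and e-stim is favoured; if moribund patients with short stays remain among controls, the effect runs the other way. Care may also have changed since 2016. Only the entry rule, taken alone, has a known sign. This objection stands in full.

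**The size is assumption, and may be trivial.** It stands that the results run from 0.00 to 5.0 days, that the largest need short or exponential stays or uniformly late entry, and that the middle case is under half a standard error. Deaths add uncertainty: the plan does not say how stay ends for a patient who dies without an intermediate-care order, so the share of short control stays is unclear. What remains is that the error is systematic and affects the quantity being estimated.

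**It can be put right later.** True: the database can be queried again. Feasibility (Aim 1) is also untouched.

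**Conclusion.** The concern holds for the entry rule taken alone. If the query is run as Section 6 is written, it compares left-truncated e-stim stays with untruncated control stays. That lengthens e-stim ICU stay relative to controls and understates any benefit, provided some comparable 2016 patients left early and are in the control mean. The direction of this mechanism is certain under that condition; the net bias of the comparison is not known.

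For uniform entry on days 2–5 the size is about 0.06 to 3.4 days over the assumed distributions, and 0.6 to 1.1 days for lognormal (10, 8). It is negligible if stays are long and entry early, and large if many similar 2016 patients left within a few days. None of these figures includes the Section 5b exclusions. It should be fixed before the control data are drawn, because the correction is cheap, but the error is not irreversible.

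**What to change.** Add to the control query in Section 6:

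1. The ICU quality group gives each candidate control an assigned ICU day and keeps only those still in the Neuro ICU on that day. The assigned days of the **retained** controls should match the distribution of actual e-stim enrolment days. Drawing days first and then dropping failures leaves 0.04–0.08 days for lognormal (10, 8) and 0.22–0.29 for lognormal (6, 6).
2. Apply those Section 5b exclusions that the database codes, as of the assigned day where possible.
3. Return the number of controls dropped, with the means.

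Stay from admission can remain the Aim 2 measure.

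This removes the truncation artefact if entry day is unrelated to severity: simulated null differences were −0.008 to +0.012 days in all ten cases (five distributions, t = d−1 or d). It should not be described as removing all bias. Under Section 5e late entry is tied to haemodynamic instability or raised intracranial pressure. In assumed cases (20–25% unstable, mean stay 12–14 versus 9–9.3 days, SD 0.75 times the mean, unstable patients entering on days 5–7 and stable ones on days 2–5), matching on day alone left about −0.15 to −0.23 days, favouring e-stim. List this residual and any uncodable exclusions as limitations.

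Cost: a slightly more complex de-identified query, run only once enrolment days are known, and the loss of early-discharge controls. At a 13.7% loss, ending with 23 controls needs 23/0.863 ≈ 27 candidates.

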## f. Consent Process

If a patient meets inclusion criteria, the study team will approach the patient or the legally authorized representative (LAR) for consent. In instances where the patient is unable to give informed consent (brain injury, sedation, etc.), the LAR will be approached for consent. Initial consent discussion will take place in a quiet private place in the Neuro ICU. The written consent form will be presented and reviewed with the patient or the LAR. At this time, the patient or LAR can ask any questions prior to enrollment. Understanding of the study will be assessed after the consent discussion and prior to enrollment by asking pertinent study related questions. When the study staff is satisfied that the patient or LAR understands, the study consent form will be signed. One copy will be given to the patient or patient's LAR, and one copy will be retained by the study team.

In the event that the patient's LAR lives at a distance, the consenting discussion may be conducted by telephone. Prior to this discussion, the LAR will be sent a copy of the consent form by mail, email, or fax. Once the LAR has received the ICF, a member of the study team will contact them by phone and go through the ICF with them, answering any questions that may arise. The LAR will sign their copy of the ICF, and may send it back to the study team by mail, email, or fax.

Version Date 7/22/19

If a patient regains the ability to consent during the study period, the coordinator will return and re-consent the patient him or herself. If the participant during the research study does not wish to continue e-stim treatments, the decision must immediately be respected. Subjects will be asked if they are willing to allow the study staff to perform a brief assessment of their recovery. If so, the subject will be considered to still be enrolled in the study, and it will be noted that the intervention was stopped early. If not, the subject will be considered to be completely withdrawn from the study, and no more data will be collected from the subject. The study team will no longer access the patient's medical record or other confidential records requiring the subject's consent.

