#### 6. Procedures Involved

[figure not shown]

Figure 1. Application of E-Stim Device

Electrical stimulation will be applied to the quadriceps muscle groups on both lower extremities simultaneously for 30 minutes at a time (Figure 1). The patient will be positioned either supine or sitting.

A Vectra Neo Clinical Therapy System (Chattanooga Group) will be used to provide the stimulation. The stimulator will be set up and taken off the patients by a member of the study team or a trained ICU staff member. The stimulation parameters will be as follows:

Electrode location: Proximal and distal quadriceps

Waveform: pulsed biphasic Pulse duration: 300-450 µseconds Pulse frequency: 35 pulses per second

Amplitude: palpable, visible quadriceps muscle contraction

On/off time: 10 seconds on, 30 seconds off Ramp up and down time: 2 seconds each

Total treatment time:  $45 \pm 15$  minutes/day, for a total of at least 5 treatments each week (Mon-Sun), until ICU discharge or at the

discretion of the research team.

At Neuro ICU discharge, a member of the study team will assess functional recovery using the modified Rankin Scale (mRS) and the Extended Glasgow Outcome Scale (GOSE). (uploaded in eIRB) Subjects who withdraw from e-stim treatment may still be assessed with these instruments at discharge, unless they request to withdraw from data collection as well. Subjects may be withdrawn from e-stim treatment without their consent if their physician or the study team decides that it is in their best interest (e.g. due to skin irritation or burns).

All procedures will be performed as part of the research study, and not as standard of care.

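### Declining a short recovery assessment after stopping e-stim also ends chart access, so the Epic-based ICU-stay endpoint of Aim 2 is usually lost for that subject

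*Combined protocol and SAP*

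**What the plan says.** Section 5f covers a participant who no longer wants e-stim. The only question put is this: "Subjects will be asked if they are willing to allow the study staff to perform a brief assessment of their recovery". When the answer is yes, the rule reads: "If so, the subject will be considered to still be enrolled in the study, and it will be noted that the intervention was stopped early". A refusal has a different effect: "If not, the subject will be considered to be completely withdrawn from the study, and no more data will be collected from the subject". Chart access ends as well: "The study team will no longer access the patient's medical record or other confidential records requiring the subject's consent". The same paragraph provides for direct re-consent: "If a patient regains the ability to consent during the study period, the coordinator will return and re-consent the patient him or herself".

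Section 6 (Procedures Involved) places the mRS and GOSE at Neuro ICU discharge. It allows subjects who leave e-stim still to be assessed, "unless they request to withdraw from data collection as well".

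Section 2 makes mRS and GOSE the exploratory Aim 3. ICU stay and intubation days form Aim 2, and ICU stay ends when step-down care is ordered in Epic. Section 7a lists the Epic record and the staff-completed instruments as two separate sources. Section 8 gives no rule for subjects who withdraw.

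**The concern.** The question in Section 5f is about a bedside procedure that serves an exploratory aim. The consequence falls on chart data that serve the efficacy aim. A patient may not want to be examined or questioned and yet have no objection to use of the record. The plan never asks that second question and treats refusal of the first as refusal of both.

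What is at stake is avoidable missing data in one group of a 22-subject pilot whose purpose is to estimate an effect size for a later randomized trial. The historical controls are pooled values extracted automatically from a database (Section 6, Historical Controls), so this rule cannot remove any of them. The loss may also be selective. Patients who regain capacity are asked in person, and their course may differ from that of patients who do not. Those who stop for other reasons may differ in the opposite direction.

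**Working it through.** **1. What each answer does under Section 5f**

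| Subject's position after stopping e-stim | Aim 3 (mRS/GOSE) | Further Epic data for Aim 2 |
|---|---|---|
| Accepts the assessment | collected | collected |
| Declines the assessment, would allow chart use | not collected | **not collected** |
| Refuses all data use | not collected | not collected |

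The middle row is the defect: the plan has no chart-only route. Section 5f does not name the instruments. That its assessment means mRS and GOSE is an inference from Section 6, which describes no other assessment of recovery.

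**2. Which Aim 2 values are lost**

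- *ICU stay.* Section 6 continues treatment to ICU discharge or at the research team's discretion. A subject who stops early therefore normally does so before the Epic order that closes the endpoint, and the value cannot be collected afterwards.
- *Intubation days.* Section 5f bars only further collection. The value is lost if the subject is still intubated, or has been extubated but the date has not been abstracted. Otherwise it can survive. Section 7c deletes repository data when consent is withdrawn, but does not say whether the study's own analysis data are affected.

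**3. The plan's own figures (Section 8, Power Calculation)**

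2 × 113 = 226; 0.20 × 226 = 45.2, taken as 45; 22 + 23 = 45. The pilot size reproduces. The 113 per group cannot be checked because no SD is stated. Solving backwards for a 3-day difference, two-sided 0.05 (sidedness assumed) and 80% power gives a common SD of about 8 days for ventilation.

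**4. Effect of losing k of 22**

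The mean over all 22 is [(22 − k) × M_ret + k × M_lost] / 22, and the mean observed is M_ret. Hence

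shift = M_ret − full mean = (k/22) × (M_ret − M_lost).

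The documents give neither k nor the difference D = M_ret − M_lost. Both are assumed here, with D of 3 to 6 days in absolute size:

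| k lost | Share of arm | Shift at 3 days | Shift at 6 days | SE of arm mean, √(22/(22 − k)) |
|---|---|---|---|---|
| 0 | 0% | 0 | 0 | ×1.00 |
| 1 | 4.5% | 0.14 | 0.27 | ×1.02 |
| 2 | 9.1% | 0.27 | 0.55 | ×1.05 |
| 4 | 18.2% | 0.55 | 1.09 | ×1.11 |

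For example, (4/22) × 6 = 1.09 days. If those lost had shorter stays, the observed e-stim mean is too long and a benefit is partly hidden. If they had longer stays, a benefit is exaggerated. For intubation, 22 is replaced by the number of subjects ever intubated, which is not given.

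**5. Sections 5f and 6 side by side**

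Section 5f infers the end of data collection from a declined assessment. Section 6 ties it to a request to leave data collection. For a subject who declines the assessment but would allow chart use, Section 5f ends collection, while Section 6 can be read as allowing it to go on.

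**The case against.** The strongest reply is that the effect is hypothetical and probably small. To be lost, a subject must both stop e-stim and refuse even a short assessment, and that may happen to nobody. With an SD near 8 days, the 95% half-width for 22 against 23 is about 4.8 days, so shifts of the size shown lie well inside the pilot's own imprecision. Treating a refusal as full withdrawal is also a cautious choice in a population with much decisional impairment, and the consent form may already separate the options. The point about size stands. The rest does not remove the defect: asking about chart use explicitly still leaves the subject free to refuse it, and a differently worded consent form would not undo the explicit rule in Section 5f.

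A reader might infer four stronger points that the documents do not support:

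- *Both Aim 2 endpoints are always lost.* Section 5f bars only further collection. A patient re-consented after regaining capacity may already be extubated, with intubation days recorded.
- *The shift can be stated as a share of the 3-day target.* That target (10 to 7 days) is for mechanical ventilation. Section 8 gives none for ICU stay.
- *Sections 5f and 6 flatly contradict each other.* Section 6 governs whether the instruments may be applied and does not address chart access for someone who declines them. Section 5f can be read as the procedure for eliciting the choice that Section 6 summarizes. The wording differs and needs reconciling; no more than that is shown.
- *Safety follow-up of a skin injury is cut off.* An injury that led to the stop would ordinarily be known by then, and Section 9 requires study-related adverse events to be reported to the IRB.

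**Conclusion.** The concern holds in limited form. Followed as written, Section 5f turns refusal of what is, by inference, the Aim 3 assessment into loss of further chart data. That usually costs the ICU-stay endpoint and sometimes costs intubation days. Only the e-stim arm is exposed.

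Each subject lost is 1/22 = 4.5% of the arm, and the cost in precision is slight. Selective loss matters more, but neither its size nor its direction can be established: the withdrawal rate and the difference between retained and lost subjects are not in the documents. The range from 0 days with none lost to 1.09 days with four lost is illustration, not an estimate, and a claim of demonstrated bias would go too far. This is a worthwhile correction because the loss is avoidable and cheap to prevent; it is not a fatal flaw.

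**What to change.** In Section 5f, replace the single question with three separate choices, and word Section 6 to match:

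- (a) stop e-stim;
- (b) decline the mRS/GOSE assessment;
- (c) withdraw permission to use the medical record.

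Only (c) ends chart data collection. A subject who chooses (a), (b) or both, but not (c), stays enrolled, and ICU stay and intubation days continue to be taken from Epic. State in Section 8 that these subjects remain in the Aim 2 comparison. Check that the consent form carries the same three choices.

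With this change, a declined assessment alone no longer costs any Aim 2 data; subjects who choose (c) are still lost, as they should be. The cost is revised wording, an IRB amendment and a slightly longer withdrawal conversation. No visits or staff are added.
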